11.3.7.3.1 ECG Numeric Variables

HR, PR, QRS, and QTcF will be summarized using descriptive statistics. The change from Baseline of these ECG parameters at each timepoint will be listed for each patient. For each timepoint of measurement, the changes from Baseline will be summarized. The relationship between HR/ECG intervals and time will be plotted.

Separate analyses will be performed in patients who are not paced and have no prolonged QRS at Baseline.

11.3.7.3.2 Categorical Analysis

The incidence count and percentage of patients with any postdose QTcF values of > 450 ms, > 480 ms, and > 500 ms will be tabulated for all patients. Patients with QTc values > 500 ms will be listed with corresponding Baseline values, $\Delta QTcF$, and Baseline and treatment HR. The incidence count and percentage of patients with $\Delta QTcF$ increase of > 30 ms and > 60 ms will be tabulated.

A separate QTcF analysis will be performed in patients who are not paced and have no prolonged QRS at Baseline.

11.3.7.3.3 Morphology Findings

New ECG morphologies for each patient not present on any ECG at Baseline for that patient will be summarized for all observation timepoints combined.

The number and percentage of patients having T-wave morphology changes and/or the occurrence of abnormal U-waves that represent the appearance or worsening of the morphological abnormality from Baseline will be reported.

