1.3 Known and Potential Risks and Benefits

There is no expectation of clinical benefit for the patients who volunteer to participate in this study. The risks of administering MYK-491 to humans are unknown, but based on nonclinical observations and the administration to healthy volunteers, MyoKardia considers that it can safely be administered if patients are carefully observed. Safety testing in other mammalian species demonstrates that dose-limiting toxicity is related only to on-target exaggerated pharmacology with development of myocardial ischemia and heart failure at high doses and after prolonged exposures. No off-target adverse effects were observed in the toxicology studies. The initial doses of MYK-491 given in this study have already been

administered as a single dose to healthy volunteers in a previous study (MYK-491-001) and shown to be well-tolerated (see above [Section 1.2](#)).

In Part 1 (single-ascending dose), patients will be admitted to the clinical research facility for dosing and will remain confined for a total of 3 days and 3 nights for each of 3 or 4 dosing periods or longer if the Safety Review Committee (SRC) believes it is important to assure the safety of the patients or to obtain robust PK and/or PD data. In no case will the patients remain confined for more than 5 days after the administration of the last dose of MYK-491.

In Part 2 (multiple-ascending doses), patients will be confined to the clinical research facility for the duration of the dosing and 2 days after dosing unless they have an ICD. Patients with the ICD will be observed frequently either in the research facility or by a home health nurse for all of the dosing, and the collection of the study parameters (plasma samples, safety labs, vital signs, and TTEs). Thus, all patients will be under close supervision, and the clinic staff will be responsible for the ongoing safety and well-being of the patients while they are confined for during the dosing periods. If a home health nurse is utilized, the nurse and site will be in daily communication to ensure safety. The initial dose for the MAD Cohort is predicted to reach exposures that have previously been observed in patients in Part 1. [REDACTED]

[REDACTED]

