4.2 Stopping Criteria

For Part 1, as each patient will receive several, ascending single doses, there are stopping criteria for which further dosing of an individual patient must be suspended, and also stopping criteria for the study to be considered by SRC.

For Part 2, as each patient will receive 9 days of study drug treatment (including 2 days of single-blind placebo and 7 days of DB active or placebo), there are dose-modification criteria and stopping criteria for individual patients, as well as stopping criteria for the study to be considered by SRC.

4.2.1 *Stopping Criteria for an Individual Participant in Part 1 (SAD)*

If the following events occur, as determined by investigator assessment, dosing of a patient must be suspended, AE/SAE forms completed as applicable, and the event reviewed by the SRC. The SRC may decide to perform selected unblinding pertaining to one or several periods for a given patient or recommend that further dosing of the patient be suspended. The following is a list of possible criteria for suspension of dosing of an individual and review of the data by the SRC:

- A patient has drug-related cardiac ischemia, as determined by investigator (Note: The whole context [ie, clinical symptoms, ECG, and cardiac biomarkers such as troponin, CK-MB, cardiac imaging, and coronary angiograms, if applicable] should be taken into account by the investigator in making that determination since patients enrolled in the study are likely to have an abnormal ECG and/or elevated and/or fluctuating troponin at Baseline in relation to their heart failure condition. This information will also be submitted for subsequent central adjudication).
- A patient has an increase in the maximal SET > 75 ms on 2 sequential TTE recordings based on site evaluations.
- A patient has clinically significant and drug-related changes in his/her vital signs that are persistent over a period of time such as a new arrhythmia, systolic BP < 90 or > 170 mm Hg, or HR < 40 or > 100 bpm. The diagnosis and clinical significance of a new arrhythmia will be adjudicated by the SRC as it relates to this stopping criterion, including core lab assessments as appropriate.
- A patient experiences a drug-related SAE (including, but not limited to, serious unexpected suspected adverse reactions [SUSARs] or coronary ischemic events).
- A patient has a QTc interval > 500 ms (Fridericia's correction, average of triplicate ECGs) not attributable to pacing or prolonged QRS duration.

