4.5 Independent Safety Adjudication

Suspected cardiac ischemia (new chest pain or angina equivalent, or new ECG changes suggestive of ischemia), new or worsening ventricular arrhythmia, and troponin elevations will be reviewed centrally by an independent safety Adjudication Committee. Adjudication package will include relevant associated clinical data and source documents including but not limited to ECGs.

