At Screening and admission, a complete physical examination will be conducted including a neurological examination (gross motor and deep tendon reflexes), and assessment of the following: general appearance, skin, head and neck, mouth, lymph nodes, thyroid, abdomen, musculoskeletal, cardiovascular, neurological, and respiratory systems. At all other timepoints, an abbreviated physical examination (pulmonary, cardiac, abdominal, and other systems related to symptoms) will be conducted.

9.4.4 *Systolic Ejection Time*

See [Section 9.2](#) for a description of assessment of SET using TTE.

9.4.5 *Electrocardiograms (12-Lead ECG)*

The 12-lead ECG should be obtained as indicated in [Appendix 1](#) and [Appendix 2](#). The actual timing of the ECGs may be modified and/or up to an additional 2 ECGs per treatment period may be requested by the SRC after review of the data from previous patients or treatment periods. In addition, the investigator may add extra 12-lead ECG assessments if there are any abnormal findings or if the investigator considers it is required for any other safety reason. If the patient has a new troponin abnormality (see [Section 9.4.9](#)) or any signs or symptoms suggestive of possible cardiac ischemia, additional ECGs should be obtained. These assessments should be recorded as unscheduled assessments. All ECG data will be sent to a central cardiac laboratory.

The investigator will judge the overall interpretation as (a) normal, (b) abnormal without clinical significance, or (c) abnormal with clinical significance. If clinically significant, the abnormality will be recorded. In addition, before each treatment period, the investigator or subinvestigator should review the available ECGs from the previous treatment periods looking for signs of ischemia. If there are signs of ischemia, continued dosing should be withheld until there is full understanding of the possible ischemic changes. Only the overall evaluation (normal/abnormal) will be recorded in the eCRF. The investigator will review the ECG and correlate abnormal findings with any other clinical findings, patient's medical history, and laboratory data to determine the clinical importance of the finding.

The 12-lead ECG abnormalities suggestive of ischemia (eg, new or worsened ST depression or new T-wave inversions), as determined by investigator, will be reviewed centrally by an Adjudication Committee.

9.4.6 *Electrocardiogram Telemetry*

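### Worsening of ST depression already present at Baseline enters no planned ECG summary, although the protocol names it as a sign of ischemia

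*Combined protocol and SAP*

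**What the plan says.** Section 11.3.7.3.3 (Morphology Findings) contains two sentences. The first: "New ECG morphologies for each patient not present on any ECG at Baseline for that patient will be summarized for all observation timepoints combined". The second promises "The number and percentage of patients having T-wave morphology changes and/or the occurrence of abnormal U-waves that represent the appearance or worsening", measured against Baseline. The ST segment is named in neither.

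Section 9.4.5 (12-lead ECG) states: "The 12-lead ECG abnormalities suggestive of ischemia (eg, new or worsened ST depression or new T-wave inversions), as determined by investigator, will be reviewed centrally". The reviewing body is the Adjudication Committee. Section 4.5 describes the adjudication trigger as "Suspected cardiac ischemia (new chest pain or angina equivalent, or new ECG changes suggestive of ischemia", with no mention of worsening.

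Section 11.2.1 lists ECG interpretation, alongside recordings and intervals, among the primary safety measures. For the investigator's own ECG reading, section 9.4.5 says: "Only the overall evaluation (normal/abnormal) will be recorded in the eCRF".

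**The concern.** Ischemia is the on-target harm that the protocol expects if the drug effect is too strong. Section 1.3 reports, from animal work, "development of myocardial ischemia and heart failure at high doses" and after prolonged exposure. Section 7.4 says that exaggerated effects may lead to myocardial ischemia.

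The plan accepts, for T-waves and U-waves, that a Baseline abnormality can get worse and that the worsening should be counted. It does not extend this to the ST segment, although section 9.4.5 lists ST depression first among its examples and explicitly includes the worsened form. What is at stake is a systematic comparison with placebo of one recognized ischemia sign, in patients whose ECG already shows it.

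**Working it through.** The plan states no figure on this point, so the check is one of coverage. Each type of ECG change is set against the two sentences of section 11.3.7.3.3.

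| ECG change after dosing | Sentence 1: absent from every Baseline ECG | Sentence 2: appearance or worsening |
|---|---|---|
| New ST depression | counted | not named |
| Same ST depression as at Baseline, now deeper | excluded | not named |
| New T-wave change | counted | counted |
| Worsened T-wave change | excluded | counted |
| New abnormal U-wave | counted | counted |
| Worsened abnormal U-wave | excluded | counted |

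Of the six rows, only the second is covered by neither sentence.

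The other analyses in section 11 do not fill it:

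- 11.3.7.3.1 summarizes HR, PR, QRS and QTcF.
- 11.3.7.3.2 tabulates QTcF thresholds and QTcF changes.
- 11.3.7.3.4 relates concentration to QTc.
- 11.3.7.4 covers ventricular arrhythmias on Holter, with supraventricular arrhythmias and heart block noted.
- 11.3.7.5 covers laboratory data, telemetry, vital signs, physical findings and concomitant medication, with no ST item.

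The investigator's recorded ECG evaluation cannot serve as a substitute. It has two levels, so a patient rated abnormal at Baseline who worsens remains abnormal.

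**Size.** The number affected is the number of patients who have ST depression at Baseline and whose same finding then worsens. The documents give neither rate. What can be shown is how much one uncounted patient weighs in a percentage table:

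- Active arm of a MAD cohort at the planned size (section 4.1.2: 6 active, 2 placebo): 1/6 = 16.7 percentage points.
- A cohort expanded to 24 at 3:1: 24 × 3/4 = 18 active, and 1/18 = 5.6 percentage points.
- Pooled MAD placebo from three cohorts at the planned size: 3 × 2 = 6 patients, and 1/6 = 16.7 percentage points.

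**The case against.** The strongest reply is that these events have other routes.

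- Section 10.1.1 requires clinically important test abnormalities that are new or have worsened, ECG included, to be captured as adverse events. Section 11.3.7.2 tabulates treatment-emergent events.
- Section 9.4.5 sends worsened ST depression to adjudication.
- Sections 4.2.1 and 4.2.4 make drug-related ischemia, judged on the whole clinical picture, an individual stopping criterion.
- The synopsis plans a count of patients with abnormal or rising troponin.
- The Safety Review Committee sees unblinded summaries, and no dosing rule depends on the morphology table.

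All of this stands. A reader might infer from section 11.3.7.3.3 that worsened ST depression goes unreported or unreviewed; the documents do not support that. What remains is that the ECG routes pass through investigator judgment, that troponin is a different measurement, and that section 11 plans no by-treatment summary of what the adjudicators conclude.

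Second, section 11.3 calls its content an outline and defers detail to an SAP before database lock. That SAP is not in the text reviewed and could close the gap. But section 11.3.7.3.3 states specific rules, and an SAP that carries them forward keeps the omission.

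Third, the term morphology is not defined. If findings are coded by lead or type, ST depression spreading to new leads could count as new. Only deepening of the same coded finding is clearly lost.

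Fourth, a reader might infer from section 4.2.1 that the situation is common, because patients are "likely to have an abnormal ECG and/or elevated and/or fluctuating troponin at Baseline". That sentence does not mention ST depression. An abnormal ECG may equally reflect pacing or a wide QRS, and even a known prevalence would count patients at risk of being missed, not patients who worsen.

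**Conclusion.** The point holds as a gap in the planned ECG tables. Worsening of the same ST depression present at Baseline is not tabulated, while section 9.4.5 treats it as a sign of ischemia and section 11.2.1 makes ECG interpretation a primary safety measure. The conclusion rests on reading the two sentences of section 11.3.7.3.3 as written, with the same coded finding at Baseline and after dosing. It needs no assumption about prevalence.

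The documents do not give the number of patients affected. They do not support a claim that the ECG tables will hide several drug-related cases. The study is descriptive, and safety decisions draw on other information. The correction is therefore worthwhile and inexpensive, but the omission does not undermine the study.

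**What to change.** 1. In the second sentence of section 11.3.7.3.3, and in the SAP, add ST-segment changes to the count of patients whose abnormality appears or worsens from Baseline. Report it by treatment and dose level from the central ECG reading. Keep the table of new morphologies.
2. Repeat the count in unpaced patients without a prolonged QRS at Baseline, a subset already planned for the interval and QTcF analyses.
3. Add a by-treatment summary of adjudicated ischemic ECG findings.
4. Have the sponsor confirm that the central laboratory codes ST change relative to Baseline, as the existing T-wave count already requires for T-waves. Write down what counts as worsening before the cohorts concerned are unblinded, since section 6.2 allows each cohort to be unblinded on its own.
5. Reconcile sections 4.5 and 9.4.5, which describe the adjudication trigger differently (new changes only, against new or worsened).

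**Cost.** A short text change, a definition of worsening, and a few extra tables. Section 9.4.5 already sends all ECG data to a central laboratory, so no new recordings are needed. The documents do not confirm that ST change is graded against Baseline there; if it is not, the stored ECGs would have to be re-read blinded. Some nonspecific ST change will be counted. The placebo column puts that in context, though coarsely with about six pooled MAD placebo patients at the planned size.

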11.3.7.3.4 Concentration-QTc Analyses

A concentration-QTc regression analysis, based on data collected from the ECG recordings after study drug administration and drug plasma concentration values for each patient at each matching timepoint, may be performed.

[figure not shown]
11.3.7.4 Holter Electrocardiograms

The interpretation and analysis of the Holter ECG data will be performed by the central ECG laboratory. Data from the 12-lead Holter recorder digital flashcard will be transmitted to the central ECG laboratory using a digital uploading system. The recordings will be reviewed for the presence of any clinically significant arrhythmias. The actual time of dosing will be communicated to the central ECG laboratory by the clinical site.

Analysis of blinded Holter recordings will be performed to assess the nature, frequency, and severity of any ventricular arrhythmias. Parameters evaluated will include but not be limited to total number of premature ventricular complexes (PVCs) during the recording period, average number of PVCs per hour, maximum number of PVCs per hour, total number of PVC pairs, total number of PVC triplets, total number of ventricular tachycardia (VT) runs (4 or more PVCs in a row), longest VT run, maximum HR during a VT run, minimum HR during a VT run, PVCs per 1000. Additional ECG abnormalities will be noted, including supraventricular arrhythmias and instances of heart block.

11.3.7.5 Other Safety Analyses

Safety laboratory data including hematology, chemistry, ECG telemetry, and vital signs will be evaluated by timepoint for the Safety Analysis population using descriptive statistics. Changes from Baseline at each postbaseline timepoint will also be assessed. Listings of patients with laboratory and/or vital sign values that are observed to be out of the reference range will be produced. Abnormal physical examination results will be listed. Concomitant medications will be summarized.

12 STUDY COMPLIANCE AND ETHICAL CONSIDERATIONS

12.1 Compliance Statement

This study will be conducted in accordance with the International Council for Harmonisation (ICH) Good Clinical Practice (GCP) guidelines; US Title 21 Code of Federal Regulations (CFR) Parts 11, 50, 54, 56, and 312; European Union (EU) GCP; cGMP; the principles enunciated in the Declaration of Helsinki; and all human clinical research regulations in the countries where the study is to be conducted.

12.2 Informed Consent

The ICFs used for the study must comply with the Declaration of Helsinki, US 21 CFR Part 50, ICH GCP guidelines, and any other local regulations. The investigator, or a person delegated by the investigator, must explain the medical aspects of the study including the nature of the study and the treatment, orally and in writing, in such a manner that the potential patient is aware of potential benefits and risks. Potential patients must be informed that participation is voluntary and that they may withdraw from the study at any time, without prejudice. Patients must give informed consent in writing.

Prior to participation in any study-related procedures, patients must sign and date an EC-approved written ICF in a language the patient can understand. The informed consent process must be conducted, documented in the source document (including the date), and the form must be signed before the patient undergoes any study-specific procedures.

The language in the written information about the study should be as nontechnical as practical and should be understandable to the potential patient. Before informed consent is obtained, the investigator should provide the potential patient ample time and opportunity to inquire about the study and to decide whether or not to participate.

All questions about the study should be answered to the satisfaction of the patient. The written ICF should be signed and personally dated by the patient and by the person who conducted the informed consent discussion. All patients will receive a copy of his/her signed and dated ICF.

12.3 Ethics Committee

The term EC used in this document refers to an IRB or Independent Ethics Committee (IEC) or equivalent. The EC must review and, if appropriate, approve the following documents, as applicable:

- Study protocol and amendment(s)
- Written ICF(s) and consent form updates
- Patient recruitment procedures/documents (eg, advertisements)
- Written information to be provided to patients

- IB and available safety information (Note: ECs do not approve IBs but are responsible for acknowledging receipt)
- Information about payments and compensation available to patients

The EC approval must be in writing, clearly identifying the study (by protocol date and/or version), the documents reviewed (including informed consent), and the date of the review. The investigator has the responsibility to provide MyoKardia with the written EC approval prior to initiating any study-related procedures.

The investigator also has the responsibility to inform the EC of the following according to the EC's policy:

- All SUSARs
- Any new information that may affect adversely the safety of the patients or the conduct of the trial
- Protocol deviations
- A synopsis of the study report upon study completion

Documentation of subsequent reviews of the study must also be forwarded to MyoKardia.

13 ADMINISTRATIVE PROCEDURES

13.1 Sponsor's Responsibilities

MyoKardia reserves the right to terminate the study at any time for any reason or for no reason. MyoKardia and the investigators will assure that adequate consideration is given to the protection of the patients' interests. MyoKardia retains the right to terminate the study and remove all study materials from a clinical site at any time. Specific circumstances that may precipitate such termination include:

- Request by Health Authority to terminate the study
- Unsatisfactory patient enrollment with regard to quality or quantity
- Significant or numerous deviations from study protocol requirements, such as failures to perform required evaluations on patients, maintain adequate study records or inaccurate, incomplete, or late data recording on a recurrent basis
- The incident or severity of AEs in this or other studies indicating potential health hazard caused by the study treatment

13.1.1 Patient Confidentiality

The processing of personal data in pursuit of this study will be limited to those data that are reasonably necessary to investigate the utility of the study medications used in this study. These data will be processed with adequate precautions to ensure confidentiality according to applicable laws.

MyoKardia ensures that the personal data are:

- Collected for a specified and legitimate purpose
- Processed fairly and lawfully
- Accurate and up to date

Explicit consent for the processing of personal data will be obtained prospectively from the participating patient.

MyoKardia, whose responsibilities require access to personal data, agrees to keep the identity of patients confidential. This confidentiality will be maintained throughout the complete data processing.

Patients will be entitled to request confirmation of the existence of personal data held by MyoKardia and will have the right to rectify erroneous or inaccurate data up until database lock.

